## **8 Response Criteria**

### **8.1 The International Working Group (IWG 2006) Response Criteria for Myelodysplastic Syndromes will be used for efficacy assessments.**

The primary efficacy parameter for these patients will be transfusion independence.

### **8.2 The secondary efficacy parameters for the study will be the remaining criteria as defined by the IWG. For each cohort, the parameters that were primary in one cohort will be secondary in the other; the following parameters also will be assessed:**

- Time to disease progression;
- Overall and progression-free survival

### **8.3 Complete remission (CR):**

**Bone marrow evaluation:** Repeat BM showing less than 5% myeloblasts with normal maturation of all cell lines, with no evidence of dysplasia (8 weeks duration). When erythroid precursors constitute less than 50% of BM nucleated cells, the % blasts is based on all nucleated cells; when there are 50% or more erythroid cells, the % blasts should be based on the non-erythroid cells.

### **Peripheral blood evaluation: (absolute values must last at least 2 months).**

- Hemoglobin: greater than 11gm/dL (untransfused patient not on erythropoietin).
- Neutrophils: 1000/ul or more (not on a myeloid growth factor).
- Platelets: 100,000 ul or more (not on a thrombopoietic agent)
- Blasts: 0%.
- No dysplasia.

**8.4 Partial remission (PR): (absolute values must last at least 2 months).**

All the CR criteria (if abnormal before treatment), except:

Bone marrow evaluation- blasts decrease by 50% or more over pretreatment but still >5%. Cellularity or morphology is not relevant.

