**Marrow CR**

Bone marrow blasts < or = 5% myeloblasts and decreased by 50% or more over pretreatment

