**Stable disease:**

Failure to achieve at least a PR, but with no evidence of progression for at least 8 weeks

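### The blast cut-points for CR, PR and marrow CR in Section 8 do not meet at 5%, and marrow CR is not separated from stable disease

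*Combined protocol and SAP*

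**What the plan says.** Section 8.1 adopts the IWG 2006 criteria, with transfusion independence as the primary efficacy parameter. Section 8.2 makes the remaining IWG criteria secondary. The categories at issue are these.

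- **CR, marrow part (8.3):** "Repeat BM showing less than 5% myeloblasts with normal maturation of all cell lines, with no evidence of dysplasia". The blood part of 8.3 adds hemoglobin, neutrophil and platelet levels, 0% blasts and no dysplasia.
- **PR (8.4):** "All the CR criteria (if abnormal before treatment), except" for the marrow part, which becomes "blasts decrease by 50% or more over pretreatment but still >5%. Cellularity or morphology is not relevant".
- **Marrow CR (unnumbered, after 8.4):** "Bone marrow blasts < or = 5% myeloblasts and decreased by 50% or more over pretreatment".
- **Stable disease (unnumbered, after marrow CR):** "Failure to achieve at least a PR, but with no evidence of progression for at least 8 weeks".

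Nothing in Section 8 says where marrow CR stands relative to PR, or whether a marrow CR is taken out of stable disease. The Synopsis, Section 5.2.2 and Section 11.2 all end treatment at week 12 for patients with no response or with stable disease, so the labels are used outside the response table as well.

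**The concern.** Response categories should cover every result and give each patient one label. Here CR stops just below 5%, PR starts just above 5%, and marrow CR includes 5%. A marrow count is often read as a whole percentage, so exactly 5% is a plausible result. The PR wording also combines a relative fall with an absolute floor, which limits who can ever qualify. Because stable disease is defined only by missing PR, a patient with a large fall in blasts can be called stable.

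Two things are at stake. Two assessors could code the same marrow differently, and a reader who takes a CR/PR table as an ordered scale of response depth could be misled. In addition, the week-12 wording refers to stable disease, and a patient who is both marrow CR and stable disease has no clear status under it.

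**Working it through.** There is no plan figure to reproduce. The check is algebra on the definitions, followed by classification of example records.

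**Inputs**, with b = pretreatment and p = post-treatment marrow blasts (%):
- CR marrow part (8.3): p < 5, normal maturation, no dysplasia.
- PR marrow part (8.4): p ≤ b/2 and p > 5, dysplasia disregarded.
- Marrow CR: p ≤ 5 and p ≤ b/2.
- Stable disease: neither CR nor PR, no progression.

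**Who can reach PR.** From p > 5 and p ≤ b/2 it follows that b ≥ 2p > 10. Enumerating b and p from 0.1% to 30% in steps of 0.1 gives 10,000 combinations that meet the PR marrow part. None has b ≤ 10, and the smallest qualifying b is 10.2.

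The clause in 8.4 about criteria abnormal before treatment adds a caveat. If b is below 5%, it could be read as waiving the blast requirement. It cannot do so for b from 5% to 10%, where the blast value already fails the CR limit. So PR is out of reach for baselines of 5-10% on either reading; below 5% this depends on how the clause is read.

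**Example records**, assuming all blood criteria of 8.3 are met for the required time and there is no progression:

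| Blasts | Fall | Marrow dysplasia | Category as worded |
|---|---|---|---|
| 12% to 6% | 6/12 = 50% | present or absent | PR |
| 12% to 5% | 7/12 = 58% | absent | not CR, not PR; marrow CR, also stable disease |
| 8% to 5% | 3/8 = 37.5% | absent | not CR, not PR, not marrow CR; stable disease only |
| 12% to 3% | 9/12 = 75% | present | not CR, not PR; marrow CR, also stable disease |
| 12% to 4% | 8/12 = 67% | absent | CR (marrow CR definition also met) |

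Rows 2 and 3 show the gap at exactly 5%. Row 4 shows the double label: dysplasia blocks CR, the floor above 5% blocks PR, and the stable disease wording has no exception for marrow CR. Row 5 shows that a deep fall meeting every CR condition is classified correctly.

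**With the CR limit at 5% or less**, rows 2 and 3 become CR and rows 1 and 5 do not change. Row 4 stays marrow CR, and leaves stable disease once marrow CR is reported apart from it.

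**The case against.** The strongest defense is that the plan adopts a published standard and that its categories, taken together, already cover most of these patients. The records 12% to 5% and 12% to 3% are marrow CR, not unclassified, and no passage ranks marrow CR below PR. That stands. What remains is that the stable disease wording captures them too, and that 8% to 5% has no other home.

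A reader might infer that the criteria generally place a deeper response below a shallower one. The documents do not support that: a deeper fall that meets all CR conditions is CR. The anomaly is confined to patients who reach 5% or less but miss CR, through residual marrow dysplasia or a value of exactly 5%. Nor does a patient going from 3% to 2% illustrate it. That is a small fall from a low start, and the abnormal-before-treatment clause may apply.

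A reader might also infer that PR will be close to empty in a low/Int-1 population. The eligibility criteria set no blast limit and the documents give no baseline distribution, so any count out of 56 would be assumed.

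It is tempting to go further and delete the floor above 5% from PR. That would make PR overlap with marrow CR, alter an adopted definition, and change who counts as stable disease at week 12. The objection to such a rewrite is sound.

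Finally, the practical reach is limited. Section 6.1.1 and the assessment schedule call for a repeat marrow only at discontinuation and only as needed to document complete response, so few patients may have data to classify. Patients like those in the table would generally still be captured through transfusion independence or erythroid response. This bears on priority; it does not resolve the inconsistent cut-points.

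**Conclusion.** The definitions in Sections 8.3 and 8.4 are inconsistent at exactly 5% blasts, and marrow CR is not separated from stable disease. Both follow from the wording alone. That PR needs a baseline above 10% is also firm for baselines of 5-10%, and depends on interpretation below 5%.

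This is a minor point. It touches secondary response categories only; transfusion independence, the signature objective and the sample size do not depend on it. The number of patients affected cannot be estimated from the documents. The example classifications assume full blood recovery for the required duration and no progression. Whether the wording departs from the cited IWG 2006 source cannot be checked from the documents, and the point does not rely on it.

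**What to change.** 1. In Section 8.3, change the CR marrow limit from strictly below 5% to 5% or less, so that CR, PR and marrow CR share one cut.
2. Leave the PR wording as it is. Note under the response table that PR, as defined, needs pretreatment blasts above 10%, and state how the abnormal-before-treatment clause applies to baselines below 5%.
3. Report marrow CR (patients not meeting CR) in its own row, separate from stable disease. Do not read the CR/PR table as ordered depth of response without that row.
4. Reconcile these definitions with the week-12 wording in the Synopsis, Section 5.2.2 and Section 11.2, so that the status of a patient labelled both marrow CR and stable disease is clear. The same applies to a patient whose label changes under item 1. Which rule governs treatment is for the investigator and sponsor to settle.

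The cost is one changed limit, one table row and a few clarifying sentences, with no new data. The small downside is that CR counts need a footnote when compared with series that use a limit strictly below 5%.

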**Marrow CR**

Bone marrow blasts < or = 5% myeloblasts and decreased by 50% or more over pretreatment

**Stable disease:**

Failure to achieve at least a PR, but with no evidence of progression for at least 8 weeks

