### 3 Schema:

All responders should continue therapy until disease progression

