### **5.2.2 Secondary Endpoints**

- Response will be evaluated **every 4 weeks during the first 12 weeks** of therapy for each of the 56 transfusion-dependent, non-del(5q) low/Int-1 risk MDS patients. Treatment will be stopped and the patient will be taken off the protocol in case of no response or stable disease by 12 weeks. International Working Group (**IWG 2006**) criteria will be used for response evaluation. The proportion of TI will be calculated and an exact 95% confidence interval of TI proportion will be estimated.
- The percent of major and minor responses in erythroid, platelets, neutrophils will also be calculated as the secondary endpoints.

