### **6.1.1.3**

The starting dose of REVLIMID® will be 10 mg days 1-28 with the first dose reduction going to 5 mg days 1-28 of a 28 day cycle. Therapy will cease if there is no response after 12 weeks. Patients responding to treatment will continue on Revlimid® until disease progression or unmanageable toxicities.

- Based on previous trials in del 5q MDS patient one hundred percent of patients reported at least one adverse event; 89% (131/148) experienced at least one grade 3/4 adverse event. Eighty percent required a dose delay and/or reduction for toxicity during the study. Thirty-four percent required a second dose delay/reduction. Dose adjustment recommendations for neutropenia and thrombocytopenia are provided in product labeling. Patients should have complete blood counts monitored weekly for the initial 12 weeks and at least monthly thereafter. Thromboembolic events were rare in the Revlimid® studies in MDS patients with deletion 5q cytogenetic abnormalities. However, in recently reported trials conducted in multiple myeloma, a significantly increased risk of deep venous thrombosis and pulmonary embolism was observed in patients treated with Revlimid® combination therapy. An elevated risk of thrombosis has also been reported when erythropoietin is used during Revlimid® treatment. The role of prophylactic anticoagulation and/or antiplatelet therapy with Revlimid® has not been adequately assessed. Any prophylactic measures should be prescribed after a careful assessment of individual risk factors.
- Patients with serum creatinine above 2.5 mg/dl were excluded from the studies. Because Revlimid® is predominately excreted by the kidney, renal function should be carefully monitored.
- Females should be advised to avoid pregnancy while taking Revlimid®. Revlimid is an analogue of thalidomide, a known human teratogen that causes severe human birth defects. Additional

reproductive toxicity studies will be performed to assess any potential Revlimid® teratogenicity. Only prescribers and pharmacists registered under the RevAssist® program can prescribe or dispense Revlimid®. Patients must agree to comply with the RevAssist® program requirements.

[figure not shown]

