**8.10 Hematologic Improvement or HI:**

All improvements must last at least 8 weeks. For a designated response (CR, PR HI) all relevant response criteria must be noted on at least two successive determinations at least one week apart after appropriate period following therapy.

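### A non-progressing patient who has transfusion independence or hematologic improvement but is short of CR/PR meets both the week-12 stop rule and the rule that responders continue

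*Combined protocol and SAP*

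**What the plan says.** **Stop rule.** The Study Endpoints part of the Synopsis, Section 5.2.2 and Section 11.2 carry the same sentence: "Treatment will be stopped and the patient will be taken off the protocol in case of no response or stable disease by 12 weeks".

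**Continue rule.** Section 6.1.1.3 says "Patients responding to treatment will continue on Revlimid® until disease progression or unmanageable toxicities", and words the stop without mentioning stable disease: "Therapy will cease if there is no response after 12 weeks". The duration and dosing cells of the Synopsis say the same. The Schema in Section 3 adds: "All responders should continue therapy until disease progression".

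**Stable disease.** The entry after PR and marrow CR in Section 8 reads: "Failure to achieve at least a PR, but with no evidence of progression for at least 8 weeks".

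**What counts as response.** Section 8.1: "The primary efficacy parameter for these patients will be transfusion independence". Section 8.10 places HI beside CR and PR: "For a designated response (CR, PR HI) all relevant response criteria must be noted on at least two successive determinations".

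**PR.** Section 8.4 requires every CR criterion that was abnormal at baseline, held for two months, with the marrow part replaced by "blasts decrease by 50% or more over pretreatment but still >5" percent.

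**Marrow.** Sections 2 and 6.1.1 schedule a marrow before treatment. A repeat is foreseen only at discontinuation of study drug, where needed to document CR.

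**The concern.** The stop sentence uses a remission category (stable disease) as its trigger, while the responses this trial mainly looks for are TI and HI, which are not remissions. Nothing in the text ranks TI or HI above stable disease. A patient freed from transfusions, without progression and without PR, is then a responder who continues and a stable-disease patient who is taken off.

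Two things are at stake. The first is disposition: followed to the letter, the stop sentence ends treatment in patients showing the effect that Section 8.1 puts first. The transfusion reviews at 16 weeks and one year (Section 8.9) would then be made off drug for those patients. The second is reporting: one patient can carry a success label and a stop label at the same visit, with no rule for which one describes the week-12 outcome.

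**Working it through.** The plan states no figure on this point, so there is none to reproduce. The check is a comparison of the rules, followed by an illustration of scale.

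**1. Rules side by side.** Take patients at week 12 with no progression for at least eight weeks. The stop sentence can be read literally (either condition stops treatment) or as *stop only if there is neither response nor stable disease*.

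| Status at week 12 | Section 3, Section 6.1.1.3, Synopsis duration and dosing cells | Stop sentence, literal | Stop sentence, neither/nor |
|---|---|---|---|
| CR or PR documented | continue | continue | continue |
| TI or HI, short of CR/PR | continue | **stop** | continue |
| No TI or HI, short of PR | stop | stop | **continue** |

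Each reading disagrees with Section 6.1.1.3 in one row. The neither/nor reading removes the conflict for TI but keeps stable patients without HI on drug. Response and stable disease together cover every patient in the table, so on that reading the sentence would stop none of them.

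**2. How easily a patient lands in the middle row.** Let b0 be baseline and b1 on-treatment marrow blasts (%). PR needs b1 ≤ 0.5 × b0 and b1 > 5, hence b0 > 10. At b0 = 10, half is 5, which is not above 5. A patient with baseline blasts of 10% or less cannot meet the PR blast clause as written.

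That alone does not make the patient stable disease, because CR also satisfies *at least PR*. But CR needs a repeat marrow as well as hemoglobin above 11 g/dL without transfusion, lasting two months (Section 8.3). No repeat marrow is scheduled by week 12, so at the decision point CR or PR will usually be undocumented.

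**3. Scale.** Inputs: 56 of 214 patients with TI in MDS-002 (Section 4.7), and N = 56 here (Section 5.2.2).

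- Rate: 56/214 = 26.2%.
- Expected TI here: 56 × 0.262 = 14.7, about 15 (95% binomial range 8 to 21).
- If a share s of these also reach CR/PR, the number in both classes is 15 × (1 − s). The documents do not give s; the values below are assumptions.

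| Assumed s | 0% | 10% | 25% | 50% |
|---|---|---|---|---|
| In both classes | 15 | 13.5 | 11.25 | 7.5 |

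**4. A limit on that scale.** Section 8.10 asks for improvements lasting at least eight weeks, so onset must come by week 12 − 8 = 4 to be complete at week 12. The median time to response quoted for MDS-002 is five weeks, and 5 + 8 = 13. Some responses will not be confirmed at the week-12 visit, and Section 4.7 does not present 26% as a week-12 rate.

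**The case against.** **Intent is visible.** Several places say responders continue. Footnote 9 of Section 2 ties later visits to having responded after 12 weeks, and the later transfusion reviews make most sense if responders stay on drug. This stands: the probable intent is that TI responders continue. It does not repair a stop sentence that appears three times in contrary terms, once in the same Synopsis as the continue rule.

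**Overlap is not an error in itself.** Stable disease sits with CR, PR and failure, while HI has its own subsections, so a patient may hold one label from each list. This also stands. The defect is the use of stable disease as a stop trigger, with no stated precedence.

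**The size can be pushed too far.** A reader might infer that every TI patient is caught. The documents do not support that: a patient with documented CR or PR is not in stable disease, and Section 2 allows unscheduled visits, at which a marrow is conceivable.

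A reader might also apply the 43% hematologic improvement rate and arrive at 24 of 56. That rate counts transfusion reductions of at least 50% (Section 4.7), whereas Section 8.11 asks for at least four fewer transfusions per eight weeks. Entry requires only two units in eight weeks, so some patients cannot meet that transfusion criterion. The 24 does not transfer.

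**Consequences can be stretched.** One might infer that sites would apply the rule in opposite ways. But Cycle 4 Day 1, which is week 12, must take place at one named center (Section 2, footnote 15). One might infer that the signature analysis is distorted. But no section ties the signature's responder label to stable disease or to the stop rule. Duration of response is not a listed endpoint either.

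**Conclusion.** The stop sentence is wrong as written. With the stable disease definition, it contradicts the continue rule for non-progressing patients who have TI or HI but are short of CR/PR. On its alternative reading it contradicts Section 6.1.1.3 for stable patients without HI. This rests on the wording alone and needs no numerical assumption.

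That the situation is likely to be common rests on the PR blast clause and on the absence of a scheduled marrow by week 12. The figure of about 15 of 56 is an upper illustration. It assumes that the MDS-002 TI rate carries over, that response is already established at week 12, and that none of these patients has reached CR/PR.

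The documents do not support the further inference that the TI analysis or the signature analysis is biased, or that responders will in fact be removed. They show that the text permits two opposite dispositions for the same patient.

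**What to change.** Reconcile the stop and continue statements in the Synopsis, Section 3, Section 5.2.2, Section 6.1.1.3 and Section 11.2 with the stable disease entry and Section 8.10, in one unambiguous week-12 sentence used everywhere. Which clinical rule that sentence expresses is for the sponsor to decide. Redefining stable disease while it remains the stop trigger would itself make that choice, so the definition and the trigger should be settled together.

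Separately, for endpoint reporting, state one order of precedence between the TI/HI labels and the CR/PR/stable disease labels, so that each patient has a single week-12 responder label.

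The cost is a wording amendment to Section 8 and to the repeated sentences. No additional data, visits or patients are needed.

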**8.5 Failure:**

Death during treatment or disease progression characterized by worsening of cytopenias, increase in the % BM blasts, or progression to an MDS FAB sub-type more advanced than pre-treatment.

**8.6 Disease transformation:**

Transformation to AML, 20% or more blasts.

**8.7 Cytogenetic response:** Requires 20 analyzable metaphases using conventional cytogenetic techniques.

**Complete:** No detectable cytogenetic abnormality, if pre-existing abnormality was present.

**Partial:** 50% or more reduction in abnormal metaphases.

**8.8 Pre-therapy assessments:** Baseline complete blood count (CBC) to which improvements will be compared was standardized using a mean value of the 4 weeks prior to the start of therapy for all patients.

**8.9 During therapy:** Responses will be assessed at 12 weeks of therapy. With regard to packed red blood cell transfusions (PRBC) and transfusion independence, the same 4 week time period was used prior to treatment to determine transfusion dependence and to obtain a baseline monthly requirement. Subsequent transfusions will be reviewed at 16 weeks, and 1-year time points.

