## **6 Investigational Plan**

### **6.1 Overall design**

#### **6.1.1 PRE, INTRA, and POST-THERAPY STUDIES:**

- Bone marrow (BM) aspirate and biopsy
  - All patients must have a BM aspirate and biopsy examination performed within 6 weeks before starting therapy. Routine diagnostic studies include morphology, histochemistry, flow cytometry, immuno-phenotyping, karyotyping, fluorescence in situ hybridization (FISH), cytogenetics. A marrow sample will be saved for the gene

- expression microarray, Luminex bead assay, and real-time PCR.
- A repeat bone marrow aspirate and biopsy will be done at discontinuation from study drug to document complete response, if needed.
  - **Medical/Medication History:** Obtained at screening. Medical history to include diagnoses and any signs/symptoms within prior 28 days. Medication history within prior 28 days and all prior treatment for MDS.
  - **Physical Exam:** Screening, monthly at Day 1 of Cycles 2, 3, and 4 and at Day 1 of every other cycle thereafter, and at discontinuation from study drug, and 30 days (+/- 7 days) following the last dose of study drug.
  - **ECOG Status:** At screening, Day 1 of Cycles 2, 3, and 4, and every other cycle thereafter.
  - **Transfusion History:** Screening, monthly at Day 1 of Cycles 1, 2, 3, each Day 1 study visit thereafter, at discontinuation from study drug, and 30 days (+/- 7 days) following the last dose of study drug.
  - **Hematology** (hemoglobin, hematocrit, RBC indices: RBC count, mean cell volume, mean cell hemoglobin, mean cell hemoglobin concentration; WBC count with differential; and platelet count) at screening, weekly during cycles 1 to 3, and then monthly (i.e., at Day 1 of each cycle) thereafter, at discontinuation from study drug, and 30 days (+/- 7 days) following the last dose of study drug.
  - **Clinical Chemistry** (creatinine, BUN, total bilirubin, alkaline phosphatase, ALT, AST, LDH, total protein) at screening, on Cycle 1 Day 1 and Cycle 1 Day 15 and on Day 1 of Cycles 2, 3, 4 and then as clinically indicated after cycle 4, at discontinuation from study drug, and 30 days (+/- 7 days) following the last dose of study drug. Thyroid stimulating hormone (TSH) will be done at screening Cycle 4 and then every 16 weeks (i.e., Cycles 8, 11, 16, etc.), and at discontinuation from study drug. T3 and T4 levels may be assessed as clinically indicated.

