  - All study participants must be registered into the mandatory RevAssist® program, and be willing and able to comply with the requirements of RevAssist®.

- Pregnancy test for women: Females of childbearing potential (FCBP)† must have a negative serum or urine pregnancy test with a sensitivity of at least 50 mIU/mL within 10 – 14 days prior to and again within 24 hours of prescribing lenalidomide. FCBP with regular or no menstruation must have a pregnancy test weekly for the first 28 days and then every 28 days while on therapy (including breaks in therapy), at discontinuation of lenalidomide and at Day 28 post the last dose of lenalidomide. Females with irregular menstruation must have a pregnancy test weekly for the first 28 days and then every 14 days while on therapy (including breaks in therapy), at discontinuation of lenalidomide and at Day 14 and Day 28 post the last dose of lenalidomide (see Appendix I: Risks of Fetal Exposure, Pregnancy Testing Guidelines and Acceptable Birth Control Methods).
- 12-Lead EKG will be performed prior to therapy.
- **MDS-Specific Tests:** at baseline and as clinically appropriate thereafter (serum B12 and erythropoietin). Optional depending on clinical situation: serum iron, total iron-binding capacity (TIBC), ferritin; flow cytometry for CD34.
- **Adverse Events, Toxicity, Concomitant Medications/Procedures:** at each study visits per Schedule of Study Assessments (Section 2), assessed by NCI Common Terminology Criteria for Adverse Events, Ver.3 Note: After Cycle 4, these assessments will be obtained every 8 weeks.
- Patient blood counts, chemistries, transfusion requirements will be reviewed at 4-week intervals with decision for continued therapy at week 12. At the discretion of the Principal Investigator, therapy will be discontinued in the event of a serious adverse event.
- Transfusion criteria: Packed red blood cells (PRBC) will be transfused in case hemoglobin falls below 8.0 Gm/dL or at a higher level in a symptomatic patient. Platelet transfusions will be given only if the patient is showing evidence of bleeding or if at risk of bleeding.

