## **6.2 Screening and Eligibility**

The Investigator is responsible for keeping a record of all subjects who sign an Informed Consent Form for entry into the study. All subjects will be screened for eligibility. Screening procedures are outlined in Section 2, Schedule of Study Assessments and unless otherwise specified, must take place within 28 days prior to initiation of therapy.

Approximately 56 of subjects with transfusion-dependent, **non-del(5q)** low/Intermediate-1 risk Myelodysplastic Syndrome will be screened for enrollment and must meet the eligibility criteria below.

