#### **Inclusion criteria**

1. Understand and voluntarily sign an informed consent form.

2. Age  $\geq$  21 years at the time of signing the informed consent form.
  3. Able to adhere to the study visit schedule and other protocol requirements.
  4. A confirmed diagnosis (using standard FAB criteria) of a myelodysplastic syndrome with low/Int-1 risk and with a non-del(5q) karyotype must be established.
  5. Patients must have transfusion dependence (at least 2 units within 8 weeks prior to starting therapy).
  6. All transfusion dependent **non**-del(5q) low/Int-1 risk patients will be eligible for treatment with Revlimid®
  7. Newly diagnosed as well as previously treated patients will be eligible
  8. Patients with primary de novo or secondary MDS will be eligible
  9. All previous cancer therapy, including radiation, hormonal therapy and surgery, must have been discontinued at least 4 weeks prior to treatment in this study.
10. ECOG performance status of 0-2 at study entry (see Appendix II).
11. Laboratory test results within these ranges:
- Absolute neutrophil count  $> 250/\mu\text{L}$
  - Platelet count  $> 30,000/\mu\text{L}$
  - Serum creatinine  $\leq 2.0 \text{ mg/dL}$
  - Total bilirubin  $\leq 1.5 \text{ mg/dL}$
  - AST (SGOT) and ALT (SGPT)  $\leq 3 \times \text{ULN}$
  - BUN  $\leq 2 \times \text{ULN}$
12. Disease free of prior malignancies for  $\geq 2$  years with exception of currently treated basal cell, squamous cell carcinoma of the skin, or carcinoma "in situ" of the cervix or breast.
13. All study participants must be registered into the mandatory RevAssist® program, and be willing and able to comply with the requirements of RevAssist®.

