**8.11 Erythroid response (HI-E):**

**Response:** For patients with pre-treatment Hb less than 11 Gm/dL, greater than 1.5Gm/dL increase in Hb; relevant reductions in units of RBC transfusion by an absolute number of at least 4 RBC transfusions/8wks compared with pre-treatment. Only RBC transfusions given for Hgb of < or = to 9.0g/dL pre-treatment will be count for transfusion response evaluation

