### 11.2 Analysis of Clinical Response

- Response will be evaluated **every 4 weeks during the first 12 weeks** of therapy for each of the 56 transfusion-dependent low/Int-1 risk MDS patients. Treatment will be stopped and the patient will be taken off the protocol in case of no response or stable disease by 12 weeks. International Working Group (**IWG 2006**) **criteria** will be used for response evaluation. The proportion of TI will be calculated and an exact 95% confidence interval of TI proportion will be estimated. The percent of major and minor responses in erythroid,

platelets, neutrophils, bone marrow and cytogenetic will also be calculated as the secondary endpoints.

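### Section 8.9 sets transfusion dependence and baseline need over 4 weeks, while inclusion criterion 5 and HI-E (8.11) work on 8 weeks, so an eligible patient can have a zero baseline and the window decides who can meet the HI-E transfusion criterion

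*Combined protocol and SAP*

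**What the plan says.** Inclusion criterion 5 (6.2.1) reads: "Patients must have transfusion dependence (at least 2 units within 8 weeks prior to starting therapy". Section 8.9, which governs response assessment, states that "the same 4 week time period was used prior to treatment to determine transfusion dependence and to obtain a baseline monthly requirement". The period it refers back to is the 4-week window that 8.8 uses to average the baseline blood counts.

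The transfusion part of HI-E in 8.11 asks for a reduction "by an absolute number of at least 4 RBC transfusions/8wks compared with pre-treatment". It adds: "Only RBC transfusions given for Hgb of < or = to 9.0g/dL pre-treatment will be count for transfusion response evaluation". Section 8.11 also lists, ahead of this and separated by a semicolon, a haemoglobin rise of more than 1.5 g/dL for patients starting below 11 g/dL.

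Section 11.2 plans the response evaluation "for each of the 56 transfusion-dependent low/Int-1 risk MDS patients", with an exact 95% confidence interval for the TI proportion. TI is the lead clinical efficacy measure, listed among the secondary objectives in 5.1.2.

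On data collection, 6.2 says that screening procedures, unless otherwise specified, "must take place within 28 days prior to initiation of therapy". Section 6.1.1 sets "Medication history within prior 28 days and all prior treatment for MDS" but gives no look-back for the screening transfusion history. Its transfusion rule is: "Packed red blood cells (PRBC) will be transfused in case hemoglobin falls below 8.0 Gm/dL or at a higher level in a symptomatic patient".

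**The concern.** The plan has two definitions of one status. A patient can be transfusion-dependent for entry and not transfusion-dependent for response. The only baseline transfusion need that the plan defines is the 4-week figure, yet HI-E is a change per 8 weeks against pre-treatment. The analyst must therefore choose between the monthly figure as it stands, a doubled version of it, and a fresh 8-week count. These choices classify some patients differently, and nothing prevents the choice from being made after the results are seen.

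At stake are the HI-E proportion and, less directly, the interpretation of TI in a patient who was already free of transfusions over the 8.9 baseline window.

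**Working it through.** The plan states no figure on this point, so there is none to reproduce. The check compares the definitions and then gives an illustration of size.

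**Inputs.** Entry: at least 2 units in 8 weeks (criterion 5). Baseline window: 4 weeks (8.9). HI-E threshold: a fall of at least 4 units per 8 weeks (8.11). Patients: 56 (11.2). TI rate in the earlier non-del(5q) trial: 56 of 214, or 26% (4.7).

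**Step 1: dependence.** Two units in weeks −8 to −5 and none in weeks −4 to −1 satisfy criterion 5. The 8.9 count is 0, so the patient has no baseline requirement and is not dependent under 8.9.

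**Step 2: HI-E transfusion part.** The largest possible fall equals the baseline count. The table compares the 8-week count with the 4-week count doubled. Doubling is an assumption.

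| Units, 8 weeks | Split, earlier/last 4 weeks | 8-week count reaches 4? | Doubled 4-week count | Reaches 4? |
|---|---|---|---|---|
| 2 | 2/0 | no | 0 | no |
| 2 | 1/1 | no | 2 | no |
| 2 | 0/2 | no | 4 | yes |
| 3 | 3/0 | no | 0 | no |
| 3 | 2/1 | no | 2 | no |
| 3 | 1/2 | no | 4 | yes |
| 3 | 0/3 | no | 6 | yes |
| 4 | 4/0 | yes | 0 | no |
| 4 | 3/1 | yes | 2 | no |
| 4 | 2/2 | yes | 4 | yes |
| 4 | 1/3 | yes | 6 | yes |
| 4 | 0/4 | yes | 8 | yes |

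The two readings disagree in both directions. If the 4-week figure is left unscaled, a patient with 4 units split 2/2 shows a baseline of 2 and cannot reach 4 either.

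**Step 3: how often the baseline is zero.** The documents give no transfusion distribution, so this is illustrative and assumes 2-unit episodes.
- Regular spacing of L weeks with random phase: max(0, 1 − 4/L) = 50%, 43%, 33%, 20% and 0% for L = 8, 7, 6, 5 and 4.
- Random timing of k episodes: 0.5^k = 50%, 25%, 12.5% and 6% for k = 1 to 4. For two or more episodes this is probably too high, because haemoglobin-triggered transfusions tend to be spaced.

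**Step 4: possible effect on TI.** Assume that 10–30% of the 56 had a single episode, half of them in the earlier four weeks: 0.5 × 0.10 × 56 = 2.8 and 0.5 × 0.30 × 56 = 8.4, about 3 and 8 patients.
- Counted as not TI: 0.26 × 53/56 = 24.6% and 0.26 × 48/56 = 22.3%, against 26%.
- Removed: the exact 95% interval widens from 24.5 points (15/56) to 25.1 (14/53) or 26.0 (12/48).

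The plan prescribes neither handling.

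**Step 5: after the change.** With one 8-week window, every patient eligible under criterion 5 has at least 2 baseline units, so a zero baseline cannot occur before the haemoglobin rule in 8.11 is applied. Patients with 2 or 3 units have a largest possible fall of 2 or 3, still below 4.

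**The case against.** The best defence is that 8.9 is leftover wording. Sections 8.8 and 8.9 are in the past tense, and 8.2 refers to cohorts that this trial does not have. That may explain the conflict. But 8.9 stands in the current response criteria and nothing overrides it.

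Three stronger readings are tempting, and the documents do not support them.

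- *Some patients drop out of the TI analysis.* No section uses 8.9 to choose the TI denominator. Sections 5.2.2 and 11.2 both evaluate each of the 56 patients, and TI is an on-treatment state that needs no subtraction from a baseline. The calculation in Step 4 assumes a rule that the plan does not contain.
- *Patients entering with 2–3 units cannot be HI-E responders.* They fail only the transfusion part, and only on an 8-week count; a doubled 4-week figure would let some of them qualify. They may also qualify through the haemoglobin rise, if the semicolon in 8.11 means or, and they can reach TI.
- *The signature endpoint is affected.* Section 11.1 sets the Luminex and PCR assays against the microarray. It names neither HI-E nor the 8.9 baseline as its reference.

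It can also be said that criterion 5 already obliges sites to look back 8 weeks. That is so for the unit count, but not for the haemoglobin at each transfusion, which 8.11 also needs.

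**Conclusion.** The point holds. Section 8.9 contradicts criterion 5 on what transfusion dependence is, and it supplies a 4-week baseline for an 8-week comparison with no rule for converting one to the other. Followed as written, it gives some eligible patients a zero baseline and changes who can meet the HI-E transfusion criterion.

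The consequence is limited to secondary efficacy endpoints. Its size cannot be computed, because the plan gives no distribution of transfusion burden; the 10–30% share above is an assumption without a source. For TI the effect is probably small: even on those assumptions it is at most about 4 percentage points, and none if all 56 stay in the denominator and are judged on treatment. For HI-E the main problem is an undefined baseline. The mismatch between the entry threshold (2 units) and the HI-E threshold (4 units) remains after the window is corrected and calls for clear reporting.

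**What to change.** 1. In 8.9, replace the 4-week period with the 8 weeks before therapy, for both transfusion dependence and baseline units.
2. In 8.11, state that this 8-week count is the pre-treatment value.
3. In 11.2, confirm that all patients eligible under criterion 5 form the TI denominator.
4. In 6.1.1, give the screening transfusion history the same 8-week look-back, recording date, units and haemoglobin before each transfusion.
5. Keep patients with 2–3 units in HI-E. Report HI-E for all patients and also by baseline burden (fewer than 4 versus 4 or more units per 8 weeks).

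The cost is mostly wording, since criterion 5 already needs the 8-week unit count. The added work is haemoglobin for weeks −8 to −5, which must come from existing records; a unit without a recorded value cannot be counted under 8.11. That rule also lowers some baselines. If 5–20% of episodes were given above 9.0 g/dL (assumed), a patient with two 2-unit episodes has a 1 − (1 − f)² = 10–36% chance of fewer than 4 countable units.

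Excluding low-burden patients from HI-E would cost more. If 30% entered with 2–3 units (assumed), the denominator would fall from 56 to 39. At an assumed response rate near 43%, the exact 95% interval would widen from 27.1 points (24/56) to 32.6 (17/39). Reporting by burden avoids that loss in the overall HI-E estimate.
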